4.2.1 Interventional (Daily Contact Testing) Arm

All those in the same first-order close contact group as the positive case will be offered the option of being tested by LFD at the start of every school day, until day 7 after being notified of being a contact¹¹. Those who do not consent to daily testing will be subject to the process outlined in Section 4.4. LFD antigen testing will be via one of two delivery models:

- 1. Supervised anterior nares swabbing, with device use assisted within a school's ATS model. The workforce for this will be trained according to national NHS T&T standard process.
- 2. Once a suitable protocol is available, at-home self-anterior nares self-swabbing under supervision of the parent / guardian (in alignment with national NHS T&T guidance). Swab samples will be self-applied at home to the LFD device and the result self-read by students under supervision of the parent / guardian, or by the parent / guardian if the student does not feel confident to use the device themselves.¹²

Those that test **negative** on the LFD negative at the start of the school day will be allowed to attend school for that day until their next test is due. It will not allow them to avoid self-isolation outside the school setting, and this will be communicated to participants using accessible, standardised materials drawing on behaviour change techniques and developed with user feedback to ensure they are credible and motivating. Participants will be required to self-isolate on days where a test has not been performed (e.g. weekends). If a non-tested day occurs at the end of Daily Contact Testing, a further negative test will be required to complete and release from the Daily Contact Testing protocol.

Those that test **positive** on the LFD test should follow the national guidance (link above) as if they have developed symptoms whilst at school and self-isolate for 10 days. If during this time they develop symptoms, the individual is asked to notify the school so this can be recorded as part of the study. They will be given an additional home PCR testing kit. They should be instructed to take a PCR swab **that day** and return it as per the enclosed instructions. This sample will be subject to genomic sequencing to allow chains of transmission to be analysis. They should also continue with any outstanding 'day 2 and 7' qRT-PCR testing (see below), as this is a research component of the study¹³. Home qRT-PCR testing kits will be provided for this purpose to remove the need to come into school for testing.

 $^{^{11}}$ For clarity, the day on which they are notified they are a contact is Day 0

¹² Initially only the in-school assisted ATS model will be available to schools. Once the at-home self-test delivery model has been finalised, participating schools will be notified and given the opportunity to switch.

¹³ For clarity, the day of their diagnosis is Day 0

As a research component of the study, Interventional Arm participants should also provide concurrent throat-and-nose swabs for qRT-PCR (on days 2 and 7 after being notified of being a close contact anterior nares swabbing may be used if throat-and-nose swabbing is not tolerated)¹³. Home qRT-PCR testing kits will be provided for this purpose by the school. Participants will be instructed that they should confirm to the school that they have taken each of the day 2 and 7 qRT-PCR tests. If the school does not receive confirmation of this by a pre-agree point in the day, they will follow up my telephone to request the test is taken. Failure to take a qRT-PCR test on days 2 and 7 (or taking it on another day) will not be considered a protocol violation.

qRT-PCR samples will be run in batches every two weeks, after which point the results will be available to participants.

Additional positive cases identified in a first-order close contact group during testing will restart the Daily Contact Testing protocol for the existing close contact group to Day 0. They should also be asked for any additional first-order close contacts, who would be eligible to start daily contact testing from that day.

4.2.3 Control (Isolation of Contacts) Arm

All those identified in the same first-order close contact group as the positive case, who would have been eligible (as part of one of the interventional arms of the study) for Daily Contact Testing should self-isolate for 10 days.

As a research component of the study, Control Arm participants should also provide concurrent throat-and-nose swabs for qRT-PCR on days 2 and 7 after being notified of being a close contact (anterior nares swabbing may be used if throat-and-nose swabbing is not tolerated)¹³. Home qRT-PCR testing kits will be provided for this purpose by the school. Participants will be instructed that they should confirm to the school that they have taken each of the day 2 and 7 qRT-PCR tests. If the school does not receive confirmation of this by a pre-agree point in the day, they will follow up my telephone to request the test is taken. Failure to take a qRT-PCR test on days 2 and 7 (or taking it on another day) will not be considered a protocol violation.

qRT-PCR samples will be run in batches every two weeks, after which point the results will be available to participants.

If an individual becomes symptomatic, they must follow national guidance and continue to self-isolate whilst awaiting results of a qRT-PCR test. The subject must restart their self-isolation period in line with national guidance.

4.3 Household Contacts

Household members of a positive index case are those who live in the same household as the positive case. These individuals should self-isolate in line with the national guidance and will not be able to enrol into the DCT component of this study: https://www.gov.uk/government/publications/covid-19-stay-at-home-guidance.

4.4 Management of those who do not Consent to DCT

Participation in the study will be voluntary, and potential participants will be provided with information on the risks and benefits as part of the consenting process. Those first-order contacts of positive cases who do not wish to be tested daily or who are unable to be tested for any reason must self-isolate in accordance with national guidance and Stay at Home guidance¹⁴ until 10 days after the they were notified of being a contact of tested positive. As a result, they will not be exposed to incremental infection risk compared to the counterfactual of the whole close contact group self-isolating.

4.5 Symptomatic Individuals

If any person develops symptoms at any time during the study, they must immediately self-isolate and order a qRT-PCR home test through the national Test and Trace symptomatic testing process¹⁵. They should follow Stay at Home guidance⁷.

4.6 Multiple Positive Cases in a School

The management of local outbreaks in a school will be managed according to the exiting national process. The school will contact the DfE coronavirus helpline ([contact] / [name]) for initial risk assessment and this will be escalated to PHE Health Protection Teams for advice managing large or complex outbreaks. The study team will also be notified. If the HPT, DPH or the school wants to stop the trial and instruct a contact group to self-isolate they should discuss this with the Trial Steering Committee. The Trial might be able to provide extra genomic analysis to determine the extent of the outbreak and help inform decision making. If DCT is stopped the IDMC should be informed.

¹⁴ COVID-19: guidance for households with possible coronavirus infection - GOV.UK (www.gov.uk)

¹⁵ https://www.gov.uk/get-coronavirus-test

4.7 Process Flow for Schools Evaluation (Intervention and Control)

Figure 3: Process flow for schools DCT evaluation interventional arm

Figure 4: Process flow for schools DCT evaluation control arm

4.8 Note on PPE

For the routine weekly active case finding PPE applicable to asymptomatic testing is appropriate. For the daily testing of contacts of a case PPE applicable to the testing of symptomatic individuals must be used.

5. Results and Data Management

5.1 Data Collection and Flows

Schools will keep their own records to help monitor who has consented, the tests taken and the results. The schools' records are to help with management of DCT and contact tracing. Some of this information will be shared with DHSC, and will include personal identifiable information. On transfer from the schools, the Data will then be stored on DHSC and NHS Digital IT infrastructure.

The LFD testing data captured through the digital mechanisms will follow the normal process including upload to NPEX and stored by NHS Digital.

Data generated by the pilot will be held, recorded, stored, and accessed on DHSC and NHS Digital IT infrastructure. Transfer of data from schools to DHSC will be encrypted using Egress which is the secure working space which has been chosen by the CISO team at DHSC to send information securely.

5.2 Data Management

Personal data generated by the study will be stored on DHSC IT infrastructure. Data Protection Impact Assessments (DPIA) will be completed. Data analysis will be conducted by NHS T&T staff, under supervision from academics at the University of Oxford.

5.3 Results Data Monitoring

During the trial the combined results of all schools in the trial will remain blinded to all except the statistical centre and the Independent Data Monitoring Committee (IDMC). The IDMC will review the overall quality, safety and efficacy of the data and make recommendations to the Trial Steering Committee on whether the trial protocol should be altered. If they have evidence beyond reasonable doubt that one strategy is clearly superior (or inferior) to another arm and that the result is likely to change public health practice, they should immediately report the unblinded data and their recommendation to the Trial Steering Committee.

Statistical Analysis of primary and secondary end-points

Conventional statistical analysis will be undertaken. Analysis will be undertaken for the primary objective at a per-school basis with comparisons to the population of control schools. Absent school days (both total and COVID-related) will be presented as a proportion of pupils (with binomial confidence intervals). Unadjusted transmission events will be measured as the incidence of all COVID-19 positive cases determined by both Pillar 2 and school directed testing. Transmission events will also be categorised as 'more likely' if they either have a similar genetic sequence (the cut off to be determined) or as a member of the same predefined school bubble.

Secondary analysis

The performance of DCT will be made at the level of each primary contact. The performance of the DCT will be compared to PCR using conventional exact binomial statistics. The extent of secondary transmission events will be analysed using Poisson statistics and the results

stratified according to the LFD and PCR results of the DCT-contact. The results can also be adjusted according to the day that the LFD becomes positive and the CT value of the PCR result.

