2.1 Study Hypotheses and Objectives

The study hypotheses are as follows:

- 1. That the intervention arm (daily contact testing) will have increased school attendance compared to the control arm (self-isolation) (i.e. superiority)
- 2. That the level of transmission of COVID-19 in the schools in the intervention arm (daily contact testing) is not inferior to (i.e. not higher than in) the control arm (self-isolation)

The primary objective of the study is to assess the effectiveness, in terms of in-school COVID-19 transmission and student / staff in-school days lost to self-isolation, of two different COVID-19 control strategies implemented at a school level using regular active case finding with lateral flow antigen tests.

Both arms of the study will include weekly active case finding of students and biweekly active case finding of staff. The arms will differ in the management of contacts of positive cases:

- (i) Arm 1: routine self-isolation of all first-order contacts of positive tests
- (ii) Arm 2: daily LFD testing of asymptomatic first-order contacts of positive tests at the beginning of the school day with self-isolation restricted to individuals with positive results.

Co-Primary End-Points

- (i) Number of school days lost from COVID-19 or contact with COVID-19 cases
- (ii) Estimated number and rate of within-school COVID-19 transmission events

Secondary End-Points

- (iii) Number and rate of positive contacts missed by daily LFD testing
- (iv) Number and rate of COVID-19 cases transmitted to the school-based and household firstorder contacts of the index case ("primary attack rate")
- (v) Number and rate of COVID-19 cases transmitted to the school-based and household second-order contacts of the index case ("secondary attack rate")
- (vi) Number and proportion of school attendees testing COVID-19 positive in weekly active case finding
- (vii) Proportion of student and staff first-order contacts who accept an offer of daily contact testing with LFD devices

Secondary objectives:

- 1. To gain knowledge on the operational aspects of this process; specifically, to understand uptake and barriers for schools and individuals as well as operational challenges.
- 2. To improve understanding of a range of behavioural factors, including reasons for participating, response to negative and positive test results, and compliance with self-isolation

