3.6 Assessment of End-Points

Please see the glossary at the start of this protocol for definitions

Co-Primary End-Points

(i) Number of school days missed among those eligible to be in school.

Daily school attendances will be obtained from the school register and absences recorded with reconciliation with COVID-19 associated absences. This will be compared between study arms, to historic schools' data, and to national schools' benchmark data collected via a survey of non-participating schools.

(ii) Estimated number of in-school COVID-19 transmission events

The number of positive cases will be obtained from the following sources:

- 1. Weekly LFD active case finding (Control and Intervention Arms)
- 2. Symptomatic individuals' NHS Test and Trace results obtained from Community Testing routine data (Control and Intervention Arms)
- 3. In-school LFD DCT testing (Interventional Arm).

Positivity rates will be reported for each source separately to facilitate like-for-like comparison between arms

Epidemiological links between cases will be obtained from the NHS Test & Trace Contact Tracing and Advice Service data base. Additional links will be obtained by membership of school-reported contact groups. Onward transmission from the index case will be determined by the following:

• Genomic sequence of virus: The additional PCR swab collected from positive individuals will be used to determine the whole genomic sequence of isolates. A sample of apparent links will be assessed with comparisons of whole genome sequencing. The diversity of genetic sequences both in the schools and the

community (routinely determined by COG) will be used to help interpret the results. Preliminary work currently undertaken will determine the appropriate genetic distance to be used to exclude a direct transmission event between individuals. This is likely to be 2 SNPs.

- Plausible epidemiological link (e.g. membership of same close contact group)
- For positive individuals identified in DCT the DMIC will review all available data to determine if the individual's infection was likely to have resulted from onward transmission from the index case, or via co-infection from an unknown 'upstream' positive or out-of-school positive case.

Secondary End-Points

(iii) Number of positive first-order contacts missed by daily LFD testing (Intervention arm only).

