The number of Covid-19-associated missed days at school is dependent on the number of positive cases identified and the number of contacts of these cases that are self-isolating. Each positive case is self-isolated for 10 days. In the control group all first order contacts will also be self-isolated for 10 days. It is expected that this trial will occur in the summer term when the number of cases in a school will be low. For instance, it is expected that in the control group about 30% of children (and their parents) will consent to participate in regular weekly active case finding testing. For the purposes of the power calculation, it is assumed that the expected number of index cases identified is about 1 outbreak/month. Each index cases will lead to identification of 50 children in their bubble who will need to self-isolate each for 10 days. The number of index cases identified is a Poisson distribution with mean 1/month with each index cases leading to 510 missed school days.

In the intervention group, it is expected that a more complex set of interactions will occur. The ability to avoid self-isolation by DCT is likely to make participation in weekly active case finding testing more

⁸ Quartagrio et al, 'Handling an uncertain control group event risk in non-inferiority trials: non-inferiority frontiers and the power-stabilising transformation' (2020)

attractive with an increase in consent to voluntary weekly active case finding testing to 60%. This in turn will lead to the identification of more positive cases with initially an expected number of 2 different index cases identified per week. However, it is expected that 70% of children will volunteer for DCT and therefore only 15 children (25% of 50) will self-isolate. In addition, about 2 contacts will be identified by LFD testing as positive during DCT (5% of 35). It is expected that these 2 children will only have contacts within the bubble and therefore they will not lead to identification of more children. In all, each index cases will lead to the index cases or 360 missed schools / month

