In addition, the intervention will lead, over time, to a decrease in transmission and therefore detection of cases through an increased identification and isolation of true positives, itself arising from an increase of uptake of weekly active case finding testing. However, this decrease will be offset by the possible increase in in-school transmission by infectious children not undertaking DCT who attend school.

It is expected that the trial will start in the Summer term with 100 schools enrolled into each arm. However, it is likely that only 50% of enrolled schools will manage to sustain the trial leaving only 50 schools in each group.

	Control Group	Intervention Group
Number of schools successfully participating	50	50
Proportion of children consenting to mass testing	30%	40-60%
Initial number of outbreaks detected/school	1/month	2/month
Number self-isolating (incl. index case and) each for 10 days	51	10-30
Number of schools in each arm	50	50

*Including index case and 2 cases in each DCT bubble of 50 children test positive and therefore need 10 days of self-isolation

Table 1: Assumptions in Power calculation

The number of schools required in each arm to determine whether school attendance has been increased by the intervention will depend on the number of children volunteering for DCT and the increase in the proportion of children consenting for weekly active case finding testing.

Assuming that 30% of the control arm participate in weekly active case finding testing, the number of schools per arm for a two month study is shown in the following table (power of 80%, two-sided alpha (0.05))

Number (per index case) in intervention group	Proportion if children consenting to weekly active case finding testing in intervention arm		
self-isolating and not undertaking DCT	40%	50%	60%
7	10	12	14
8	11	13	15

911141810121521111317241214192913152236141826451518305816203579172343112182653170192967172033871172138117				
11 13 17 24 12 14 19 29 13 15 22 36 14 18 26 45 15 18 30 58 16 20 35 79 17 23 43 112 18 26 53 170 19 29 67	9	11	14	18
12 14 19 29 13 15 22 36 14 18 26 45 15 18 30 58 16 20 35 79 17 23 43 112 18 26 53 170 19 29 67 17 20 33 87 112 21 38 117 117	10	12	15	21
13 15 22 36 14 18 26 45 15 18 30 58 16 20 35 79 17 23 43 112 18 26 53 170 19 29 67 1 20 33 87 1 21 38 117 17	11	13	17	24
14 18 26 45 15 18 30 58 16 20 35 79 17 23 43 112 18 26 53 170 19 29 67	12	14	19	29
15 18 30 58 16 20 35 79 17 23 43 112 18 26 53 170 19 29 67	13	15	22	36

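### Section 5.3 expresses absent school days as a proportion of pupils with binomial intervals: the units do not match, the ratio can exceed 1, and it grows with the length of observation

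*Protocol*

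**What the plan says.** Protocol section 2.1 defines co-primary (i) as a count of days: "Number of school days lost from COVID-19 or contact with COVID-19 cases". Section 3.6 restates it as "Number of school days missed among those eligible to be in school" and gives the source: "Daily school attendances will be obtained from the school register and absences recorded with reconciliation with COVID-19 associated absences". The same section plans to compare this endpoint between arms, with historic school data, and with a national benchmark from a survey of non-participating schools.

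The analysis text in section 5.3 first sets the unit: "Analysis will be undertaken for the primary objective at a per-school basis with comparisons to the population of control schools". It then sets the summary: "Absent school days (both total and COVID-related) will be presented as a proportion of pupils", and specifies binomial confidence intervals for it.

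Two statements in section 3.9 bear on this. Control index cases follow a Poisson distribution with mean one per month, "with each index cases leading to 510 missed school days". On retention, "it is likely that only 50% of enrolled schools will manage to sustain the trial".

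**The concern.** The numerator counts days and the denominator counts people. A binomial proportion needs each unit of the denominator to contribute at most one event, but section 3.9 itself charges ten days to every isolating pupil. Two things follow. The ratio has no upper bound of 1, and above 1 no binomial interval exists. The ratio is also a cumulative total per pupil, so it grows with the number of school days a school is observed.

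The endpoint matters because section 3.9 powers the trial on attendance and makes superiority there the condition for asking an independent committee to judge the transmission result. Unequal observation is foreseeable, since half the schools are expected not to sustain the trial. The planned external comparisons also involve sources that need not cover the same length of time. Days per pupil cannot be compared across such sources without a time denominator.

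**Working it through.** **Inputs from the Protocol**
- Control (3.9): index cases Poisson, mean 1 per month; 51 people isolating for 10 days per index case.
- Intervention (3.9): 15 pupils isolating plus the index case and 2 positive contacts, so 18 people for 10 days. Table 1 gives 2 outbreaks per month. The prose says 2 per week, but the stated 360 days per month requires 2 per month.
- Study length: two months (3.9, text before Table 2).

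**Assumptions**
- Pupils per school: not given. The only clue is a year group of over 250 (section 1); five to seven such groups would be 1,250 to 1,750. The range used is 500 to 1,750.
- About 20 school days per month.

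**The plan's own figures first**
- 51 × 10 = 510 days per control index case; 2 × 18 × 10 = 360 days per month in the intervention arm. Both agree with section 3.9.
- Table 2 is recovered by comparing mean missed days per school over two months under a compound Poisson model (mean λm, variance λm²). Example, 27 isolating at 40% consent: control λ = 2, m = 51; intervention λ = 2 × 40/30 = 2.67, m = 27 + 3 = 30. Means are 102 and 80, variances 5,202 and 2,400. The normal approximation gives 7.85 × 7,602 / 22² = 123.3, so 124; the noncentral t gives 125, as printed. Across the 49 legible cells the t version is within one school of the table in all but one, which differs by two.
- Table 2 therefore rests on counts per school with equal two-month follow-up and is not affected by this point.

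**Days over pupils, COVID-related absence, two months**

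Expected days: control 2 × 510 = 1,020; intervention 4 × 180 = 720. The probability that the ratio exceeds 1 is the Poisson tail (mean 2 or 4) from the smallest number of index cases whose days exceed the roll.

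| Pupils (assumed) | Control ratio | P(ratio > 1) | Intervention ratio | P(ratio > 1) |
|---|---|---|---|---|
| 500 | 2.04 | 87% | 1.44 | 76% |
| 750 | 1.36 | 59% | 0.96 | 37% |
| 1,000 | 1.02 | 59% | 0.72 | 22% |
| 1,250 | 0.82 | 32% | 0.58 | 11% |
| 1,750 | 0.58 | 14% | 0.41 | 1% |

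For example, at 1,000 control pupils two index cases suffice (1,020 > 1,000), and P(Poisson(2) ≥ 2) = 1 − 3e⁻² = 0.594.

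**Sensitivity to weekdays.** The 510 counts all ten isolation days as school days. With 7 or 8 weekdays each, an index case costs 51 × 7 = 357 or 51 × 8 = 408 days. Exceeding 1,000 then needs three index cases (32% instead of 59%), and exceeding 1,250 needs four (14% instead of 32%).

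**Total absence.** The same sentence covers it. Over about 40 school days the ratio passes 1 once absence exceeds 1/40 = 2.5%, whatever the school size.

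**Observation time.** At 1,000 pupils the expected control ratio is 1,020/1,000 = 1.02 over two months and 510/1,000 = 0.51 over one. On pupil-days it is 1,020/40,000 = 2.55% and 510/20,000 = 2.55%. The intervention rate is 720/40,000 = 1.80%.

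**The case against.** The strongest reply is that this is loose wording. The terms proportion and binomial make sense only for a bounded quantity, and section 3.6 takes attendance daily among those eligible, so the authors may well have meant eligible pupil-days. The sentence also describes presentation, while the sentence before it sets a per-school comparison, and offsets are commonly left to the SAP. Much of this is fair. But the protocol does name a denominator, it is the wrong one, and neither section 2.1, 3.6 nor 3.9 supplies another. The charitable reading is the proposed correction.

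Four stronger readings are tempting and should not be drawn:
- *The statistic cannot be computed.* Days per pupil can always be computed, and over a fixed period it is a legitimate mean. Only the binomial interval fails, and only above 1.
- *The plan's own figures show that it usually exceeds 1.* This needs a school size the protocol does not give, is less frequent in the intervention arm except in very small schools, and weakens if only weekdays count.
- *The attendance comparison is biased.* One can construct a bias: if stopping schools are observed for half the period, and 40% stop in one arm against 60% in the other, the mean observed shares are 0.8 and 0.7, a ratio of 1.14. Those stopping rates and the half period are hypothetical. Section 3.9 assumes equal attrition, leaving 50 schools per arm, and Table 1 counts only schools that participate successfully.
- *Superiority is tested on this displayed ratio.* Section 5.3 does not establish that; section 3.9 describes the primary endpoint as the number of missed days.

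**Conclusion.** The point stands as an error in a stated rule. The summary prescribed for co-primary (i) has mismatched units, is unbounded, and is proportional in expectation to the time observed. None of that depends on an assumption. The frequency with which it exceeds 1 does: it rests on assumed school sizes and on taking 510 days at face value. For total absence it needs only more than 2.5% absence over an assumed 40 days.

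If observation time is similar in the two arms, as the protocol assumes, the consequence is extra between-school noise and loss of comparability with the historic and national data in section 3.6, rather than bias between arms. The sample size is untouched. The correction is worth making because the endpoint is co-primary and the change costs almost nothing.

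**What to change.** In section 5.3, define the summary for co-primary (i) as absent days divided by eligible pupil-days on the register during each school's observed trial period (eligible pupils summed over the school days observed), for total and for COVID-related absence. State that the per-school comparison between arms uses the same denominator, or log pupil-days as an offset. Count only school days in the numerator, so that it matches the denominator.

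The cost is one or two sentences. The daily register in section 3.6 already supplies the data, and there is no material downside. The new denominator does not by itself make a binomial interval valid, because absences cluster within pupils and bubbles; that is a separate point.

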3.2 Methods

3.1 Overview of Design

This is a pragmatic cluster randomised controlled study. Eligible participating schools will be stratified according to institution type, size, Free School Meal prevalence and local COVID-19 prevalence and randomly allocated into the two study arms. A schematic summarising the study design and participant sub-groups can be found in Figure 2 below.

Regular Active Case Finding. In schools participating in either arm of the study, consent will be obtained from adults/parents/guardians for voluntary weekly testing of all students and biweekly testing of all staff⁵. Tests will be performed with lateral flow devices (LFD)*, and results will be reported in the NHS Test and Trace database. LFD Tests will initially be performed as an assisted test in a school setting. Once a reliable protocol for home testing and recording of LFD is available, schools will be offered the option for at-home self-testing for weekly case finding.

Individuals who test positive will self-isolate and identify first-order contacts according to national guidelines. In addition, symptomatic cases who test positive via NHS Test and Trace, and asymptomatic cases who test positive outside the in-school testing regimen will self-isolate and report their results to the school. All individuals with a positive test will be asked to provide a PCR swab test for genomic sequencing.

1. Intervention (Daily Contact Testing) Arm

a. Public Health Intervention: Consenting first-order contacts of a COVID-positive index case will receive daily contact testing for 7 days from the point of being notified they are a close contact⁶. This will consist of a daily LFD*. Those that receive a negative LFD result can attend school for that day, but other than travelling to and from school will be instructed to continue to self-isolate outside the school setting. Those that receive a positive LFD result should not attend school and will be instructed to self-isolate for 10 days according to national guidelines. The contacts of all first-order contacts (i.e. 'second-order contacts') will be identified to allow the determination of secondary attack rate.

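### Binomial confidence intervals for absent school days ignore clustering of absence in outbreaks and schools; on the protocol's outbreak model they are about 23 (control) and 13 (intervention) times too narrow on pupil-days

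*Protocol*

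**What the plan says.** Schools are the randomised units, and section 3.1 has them "stratified according to institution type, size, Free School Meal prevalence and local COVID-19 prevalence". The first co-primary endpoint in section 2.1 is "Number of school days lost from COVID-19 or contact with COVID-19 cases".

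Two consecutive statements in section 5.3 govern its analysis. The first sets the level: "Analysis will be undertaken for the primary objective at a per-school basis with comparisons to the population of control schools". The second names the only measure of uncertainty given for this endpoint: "Absent school days (both total and COVID-related) will be presented as a proportion of pupils (with binomial confidence intervals". Nothing in the protocol adjusts that interval for clustering or overdispersion.

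Section 3.9 describes how absence is expected to arise in control schools: "The number of index cases identified is a Poisson distribution with mean 1/month with each index cases leading to 510 missed school days". For the intervention arm it gives 15 contacts isolating and 2 found positive by daily testing for each index case, and 360 missed days per month.

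**The concern.** Under section 3.9 the random quantity is the number of outbreaks in a school. Once an outbreak occurs, a whole block of days is lost together. A binomial interval counts each day in the block as separate evidence, so it reports far more information than the trial holds.

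There is also a mismatch of units: a count of days over a number of pupils is not a binomial proportion. The method must therefore be read with either pupil-days or pupils as the trials. Both readings are checked below.

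At stake are the published limits for one of the two endpoints that carry the trial's conclusion. Readers would take large chance variation between schools for precise estimation.

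**Working it through.** **Inputs from section 3.9**
- Control: 1 outbreak per school per month, 51 people isolating for 10 days, so c = 51 × 10 = 510 days per outbreak.
- Intervention: 15 isolating + 2 positive in daily testing + 1 index case = 18 people, so c = 180 days. The stated 360 days per month equals 2 × 180, which matches the 2 outbreaks per month in Table 1. The text's mention of 2 index cases per week does not fit 360; the rate barely affects the ratios below.
- Two-month study, 50 schools per arm, 80% power, two-sided 0.05.

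**Assumptions, not in the protocol:** 1,000 pupils and 40 school days per school, or 40,000 pupil-days; range 500 to 1,500 pupils.

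**Step 1. Reproduce Table 2** (15 isolating, 60% consent; stated 58 schools per arm). In units of 10 days per school over two months:
- Control: mean 2 × 51 = 102; variance 2 × 51² = 5,202.
- Intervention: mean 4 × 18 = 72; variance 4 × 18² = 1,296.
- n = (1.960 + 0.842)² × (5,202 + 1,296) / (102 − 72)² = 56.7, so 57 by the normal formula. The two-sample t version gives 58, as stated.

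Over all 49 cells, the t version is within one school in 48 and two schools off in one. The sample size therefore agrees with a comparison of schools whose variance comes from the outbreak model.

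**Step 2. Ratio of true to binomial standard error, pupil-days as unit.** With μ outbreaks per school, the true variance of days lost is μc². The binomial variance is μc(1 − p), where p is the proportion of pupil-days lost. The ratio of standard errors is √(c / (1 − p)). It does not depend on the number of schools.
- Control: p = 1,020 / 40,000 = 0.0255; ratio √(510 / 0.9745) = 22.9. Without the (1 − p) term, √510 = 22.6.
- Intervention: p = 720 / 40,000 = 0.018; ratio √(180 / 0.982) = 13.5. Without the term, √180 = 13.4.
- School size of 500 to 1,500: 22.8 to 23.2 and 13.5 to 13.7.
- Table 1's intervention range of 10 to 30 isolating: √100 = 10.0 to √300 = 17.3.
- If 10 days of isolation cost only 7 school days (assumption): √357 = 18.9 and √126 = 11.2.

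**Step 3. Pupils as unit.** Replace c by the number of people per outbreak and p by the proportion of pupils ever absent.
- Control: √(51 / (1 − 0.102)) = 7.5; range 7.1 to 8.0 for schools of 500 or more.
- Intervention: √(18 / (1 − 0.072)) = 4.4; range 4.2 to 4.6.

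**Step 4. Coverage of a nominal 95% interval on pupil-days, 50 schools.**
- Control: half-width 1.96 × √(50 × 1,020 × 0.9745) = 437 days, less than the 510 days of one outbreak. The interval covers the truth only if exactly the expected 100 outbreaks occur. The Poisson probability of that is 0.040; simulation gave 3.9%.
- Intervention: half-width 1.96 × √(50 × 720 × 0.982) = 369 days, or about two outbreaks of 180. It covers for 198 to 202 outbreaks when 200 are expected: probability 0.140; simulation gave 13.9%.

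**The case against.** The strongest reply is that the binomial sentence describes presentation only. The sentence before it places the primary analysis at school level, Table 2 agrees with a school-level comparison, and the between-arm model may properly be left to a statistical analysis plan. As far as it concerns the between-arm test, this stands.

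A reader might infer that the superiority claim on attendance rests on the binomial variance, so that chance differences would usually be declared significant. The protocol specifies no such test. If a pooled binomial comparison were used, two identical arms would differ significantly in about 92% of trials under the assumptions above. A t-test on school values, one natural reading of the per-school sentence, rejects in 5.0%. The 92% is a warning about one possible reading and not a property of the plan.

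Nor would the independent committee in section 3.9 be misled by this interval. It is asked to judge the interval for transmission events.

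The reply does not rescue the interval. The protocol names the method, so this is not detail left for later. Giving one binomial interval per school does not help, because the ratio in step 2 is the same for one school as for fifty.

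Three limits on scope also stand. The 23 and 13 need pupil-days as the unit, which is an inference. They apply to COVID-related absence only, since the outbreak model does not describe total absence. And section 5.3's other plain methods ("The performance of the DCT will be compared to PCR using conventional exact binomial statistics" and "The extent of secondary transmission events will be analysed using Poisson statistics") likewise mention no clustering, but no size has been worked out for them, and the missed-day argument does not carry over. The difference between section 2.1 and the wording in section 3.6, "Number of school days missed among those eligible to be in school", is a separate question of endpoint definition, as is the place of staff days.

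**Conclusion.** The point holds for the intervals that section 5.3 names. For COVID-related absence they are too narrow by a factor of about 23 in control and 13 in intervention on pupil-days (10 to 17 in intervention over Table 1's range), or about 7 to 8 and 4 to 5 on pupils. They are much too narrow on every reading checked. The factors rest on the protocol's own outbreak sizes and Poisson outbreak counts, and hardly on the assumed school size; the coverage figures of about 4% and 14% also need 1,000 pupils, 40 school days and 50 schools per arm.

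The stated interval is inconsistent with the per-school analysis beside it and with the sample size calculation. It should be corrected because it is a named method for a co-primary endpoint. Whether the between-arm test shares the fault cannot be told from the protocol; if it did, its type I error would be far above 5%.

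**What to change.** In section 5.3, replace the reference to binomial confidence intervals. State that days lost will be expressed per enrolled pupil-day, and that intervals for each arm and for the difference between arms will come from school-level summaries or from a model with an overdispersed or school-robust variance. The comparison should adjust for the four stratification factors in section 3.1. State also that the test of superiority uses the same variance, which removes the doubt described above. The exact model can be left to the statistical analysis plan.

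The cost is a change of wording and visibly wider intervals. On the evidence of Table 2, the planned number of schools already allows for variance between schools, so this change alone gives no reason to alter it.
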